4. STUDY DESIGN AND RATIONALE

4.1. Description of Study Design

This registry study is a one-year, one-visit, observational, prospective, open-label, two-arm, multi-center, multi-national, post-market study. Approximately 300 patients who have recently been fitted with the ACUVUE® OASYS with Transitions™ (Test) and approximately 300 patients who have recently been fitted with spherical non-photochromic reusable marketed silicone hydrogel contact lenses (of any brand) (Control) will be enrolled in the study, a total of 600 subjects. The goal is for a sample size of 480 subjects (~240/arm) after subjects who withdraw or are lost-to-follow-up.

At Visit 1, each subject will be first consented to participate in the study. The ECP will then complete the paper ECP Registration Questionnaire (ERQ) for the given consented subject and collect his/her demographics and baseline information. Participants who meet eligibility criteria, will be asked to complete the Patient Registration Questionnaire (PRQ). At the end of the visit, registrants will be instructed to complete the survey follow-up questionnaire online at 2-weeks (day 10-30), 4-months (day 110-150) and 12-months (day 345-395) from Visit 1

(day 0). The registrants will receive an email reminder and link to the online questionnaire (Kiosk) prior to each evaluation period. Follow-up on events reported at each evaluation period will be completed by the Recruiting Practitioner/PI.

Country specific Good Clinical Practice (GCP) standards, laws, and applicable regulations were reviewed in designing the clinical study protocol to ensure compliance in the management of the clinical trial and to protect the rights and interest of subjects.

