2.2. Endpoints

All of the primary and secondary endpoints will be assessed using the follow-up questionnaire administered at 2-weeks, 4-months and 12-months after the enrollment visit (Visit 1).

Primary endpoints

Vision Satisfaction in Bright Lighting

Subjects will be asked to evaluate their vision satisfaction in bright lighting by rating their level of agreement with the statement “I was satisfied with the quality of my vision in bright lighting with these contact lenses” using a 5-point agreement Likert scale (1: Strongly Disagree, 2: Disagree, 3: Neither Agree nor Disagree, 4: Agree and 5: Strongly Agree).

Secondary endpoints

Overall quality of vision

This will be assessed subjectively using the item “I am satisfied with the overall quality of my vision with these contact lenses”. The item uses a 5-point agreement scale (1: Strongly Disagree to 5: Strongly Agree)

Pulfrich Effect

This will be assessed subjectively using the item “While wearing these lenses, my depth perception of moving objects has NOT been impacted”. Subjects who disagree or strongly disagree with the statement will be considered to have experienced the Pulfrich effect.

Overall comfort

This will be assessed using the item “How would you rate the overall comfort of these contact lenses?”. The item uses the 5-point satisfaction scale, 1: Excellent, 2: Very Good, 3: Good, 4: Fair and 5: Poor.

Reported serious and significant ocular adverse events:

Incidence rate serious and significant ocular adverse events during the study period will be calculated (in 100 patient-year) using all available data from the entire study.

Other endpoint(s):

1. Overall satisfaction
2. Cosmetic appearance assessment
3. Lens storage compliance
4. Reasons for discontinuations
5. All reported ocular and non-ocular adverse events
6. Other subjective assessments (indoor performance, overall opinion, average wear time, etc.)

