2.3. Hypotheses

Primary Hypotheses

Subjects wearing JJVC senofilcon A contact lenses with photochromic additive (ACUVUE® OASYS with Transitions™ contact lenses) will have superior vision satisfaction in bright lighting compared to subjects wearing non-photochromic reusable silicone hydrogel contact lenses over a period of one year.

Secondary Hypotheses

1. Subjects wearing JJVC senofilcon A contact lenses with photochromic additive (ACUVUE® OASYS with Transitions™ contact lenses) will have superior vision satisfaction compared to subjects wearing non-photochromic reusable silicone hydrogel contact lenses at 12-month evaluation. This hypothesis will also be tested at 2-week and 4-month evaluation periods.
2. Subjects wearing JJVC senofilcon A contact lenses with photochromic additive (ACUVUE® OASYS with Transitions™ contact lenses) will have superior overall quality of vision compared to subjects wearing non-photochromic reusable silicone hydrogel contact lenses over a period of one year. This hypothesis will also be tested at each evaluation period.
3. Subjects wearing JJVC senofilcon A contact lenses with photochromic additive (ACUVUE® OASYS with Transitions™ contact lenses) will have superior overall comfort compared to subjects wearing non-photochromic reusable silicone hydrogel contact lenses over a period of one year. This hypothesis will also be tested at each evaluation period.

No hypotheses are formulated about Pulfrich effect or, serious and significant ocular adverse events (AEs). The following will be calculated by arm:

1. Proportion of subjects who experienced the Pulfrich effect at each evaluation period.
2. Incidence rate of serious and significant ocular AEs (in patient-year)

3. Proportion of subjects with at least one reported serious or significant ocular AE at each evaluation period.
4. Proportion of eyes with at least one reported serious or significant ocular AE at each evaluation period.
5. Proportion of all reported serious and significant ocular AEs at each evaluation period.

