3.2. Inclusion Criteria

Potential subjects must satisfy all of the following criteria to be enrolled in the study:

Inclusion Criteria after Screening:

1. Contact lens neophytes or those who have recently (i.e. within last 2 months) begun the use of a new reusable silicone hydrogel lens type and have purchased a supply of lenses.
2. A minimum age of 18 years, with no maximum age.
3. The registrant must read and sign the Informed Consent form.
4. The registrant must appear able and willing to adhere to the instructions set forth in this clinical protocol.

For clarification, non-neophyte subjects may include previous wearers of any type of soft contact lens (e.g. daily disposable), however, the new lens type must be a reusable silicone hydrogel. Also, non-neophyte subjects may have previously worn soft contact lenses at any point in time; in other words, it is not necessary for recently refitted subjects to have transitioned from their old to new lenses without a break in wear.

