3.4. Enrollment Strategy

Study subjects will be recruited from the clinical site's subject database and/or utilizing Independent Ethics Committee (IEC) or Institutional Review Board (IRB) approved materials.

Site recruitment based on actively prescribing a new device is a method that has been used in two prior post-market surveillance studies for FDA.^{5,6} Proposed regions include but are not limited to areas within the United Kingdom (UK), Spain, Netherlands and Germany. Regions will be replaced or supplemented if there is inadequate response to invitations to participate.

The Principal Investigator and CRO will recruit sub-investigators, referred to as ‘Recruiting Practitioners’ throughout this document at clinical sites. Clinical sites in the selected regions that are actively prescribing the ACUVUE® OASYS with Transitions™ lenses will be invited to participate as Recruiting Practitioners. Recruiting Practitioners will be allowed a maximum of 50 registered wearers per site, so that no one site will contribute more than 25% of the sample population in a given country. The study anticipates unequal enrollment across the sites, as their rate of prescribing ACUVUE® OASYS with Transitions™ will vary considerably. Unequal enrollment should reflect the population exposures to the Test lens and follows the tenets of surveillance. A convenience, rather than random, sample is necessary for the study because ACUVUE® OASYS with Transitions™ contact lenses have not yet been widely launched and are only available to some eye care practitioners. Thus, active prescribers of ACUVUE® OASYS with Transitions™ lenses will be invited to participate within each region in order to provide a large enough sample size for the study.

Within sites, wearers of ACUVUE® OASYS with Transitions™ lenses will be invited to participate without regard to any demographic or other ocular features. Wearers will be registered after they have recently (i.e. within last 2 months) received a prescription for and a supply of ACUVUE® OASYS with Transitions™ lenses.

The study design also allows an unconstrained relative proportion of ACUVUE® OASYS with Transitions™ lenses within a site in order to reflect the exposure profile present in that site. When the study has enrolled 300 Test lens subjects, enrollment will be actively curtailed but leaving the enrollment open to the other lens type until complete (or vice versa).

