7.2. Detailed Study Procedures

Prior to Visit 1, the registrant is fitted with the Test or Control lens, and purchases a supply of lenses.

VISIT 1

Visit 1: Registration		
Step	Procedure	Details
1.1	Study Explained	Recruiting Practitioner or Staff explains participation in Registry
1.2	Statement of Informed Consent	Registrant completes Informed Consent (IC) Note: The subject must be provided with a signed copy of this document.
1.3	Demographics	Record the subject's year of birth, age and gender
1.4	ECP Registration Questionnaire (ERQ)	The Eye Care Practitioner (ECP) completes a paper ECP Registration Questionnaire (ERQ) for each Registrant recording the following information (steps below) as source documentation.
1.5	Iris Color	The investigator will record the subject's iris color based on the 15-color scale provided (Appendix C).
1.6	Contact Lens History	Experienced CL wearer (Yes/No) If Yes, number of years total, last CL brand, replacement frequency, and when last used.
1.7	Contact Lens Details (New lenses)	Brand (full name), base curve, powers, recommended replacement period, recommended care system, and planned usage (Full/Part-Time). If part-time, number of days/week.
1.8	Reason for Lens Selection	Up to three reasons for selection of lens type to be indicated by the ECP investigator.
1.9	Eligibility after Screening	All responses to Screening Inclusion Criteria questions must be answered "Yes" and all responses to Exclusion Criteria must be answered "No" for the subject to be considered eligible.
1.10	Patient Registration Questionnaire (PRQ)	Registrants complete the Patient Registration Questionnaire. When possible, the PRQ should be completed on the same day as the ERQ. Please refer to [REDACTED] attached to this protocol (Appendix D)
1.11	Contact Details	Subject provides contact details to CRO by texting study ID number and email address to the dedicated Kiosk Set-Up texting line that will be provided to them by the site.

Visit 1: Registration		
Step	Procedure	Details
1.12	Kiosk Set-up	On receiving, the subjects contact details, subjects Kiosk will be set up and reminders will send to subjects.

2-Week Questionnaire		
Step	Procedure	Details
2.1.	Reminder	Registrant receives an email reminder and link to online follow-up questionnaire (Kiosk). In cases where a subject fails to respond to the email prompts, at least two additional emails will be sent, approximately 1 week apart. As a final resort a text message may be sent with a similar prompt.

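### Ratings are timed from Visit 1, but lenses may have been started up to two months earlier, and time on lens is neither a listed Visit 1 field nor a named model term

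*Combined protocol and SAP*

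**What the plan says.** **Time origin.** Section 4.1 sets the questionnaires at "2-weeks (day 10-30), 4-months (day 110-150) and 12-months (day 345-395) from Visit 1", which is day 0. Section 2.2 and Table 2 use the same origin for every primary and secondary endpoint.

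**Wear before day 0.** Section 7.2 states: "Prior to Visit 1, the registrant is fitted with the Test or Control lens, and purchases a supply of lenses". Inclusion criterion 1 (section 3.2) admits contact lens neophytes or "those who have recently (i.e. within last 2 months) begun the use of a new reusable silicone hydrogel lens type". For the Test arm, section 3.4 adds: "Wearers will be registered after they have recently (i.e. within last 2 months) received a prescription for and a supply of" the Test lens.

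**Data on the new lens.** Step 1.7 of section 7.2 lists "Brand (full name), base curve, powers, recommended replacement period, recommended care system, and planned usage (Full/Part-Time"), with days per week for part-time users. The question in step 1.6 about when lenses were last used concerns the previous brand.

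**Analysis.** The primary model in section 14.5 has group, evaluation period and their interaction, with site as a random effect. It adjusts for baseline values, country, age, gender and race where appropriate. A propensity score from logistic regression is also planned, without a list of its covariates. Secondary hypothesis 1 in section 2.3 is framed at 12 months, and then adds: "This hypothesis will also be tested at 2-week and 4-month evaluation periods".

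**The concern.** A subject registered on the day of dispensing and one registered two months later both count as day 0. At the 2-week rating the first may still be adapting to the lens, while the second is an established wearer who has already chosen to continue. Subjects who gave up a lens before being invited may never enter the registry, so a longer gap before registration also selects for people who tolerated the lens.

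This matters for the comparison only if the gap differs between arms. Nothing in the design balances it, because lens choice is not randomised. Sections 4.2 and 14.5 themselves warn that the arms may differ widely at baseline. The enrolment rules leave room for a difference in timing:

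- Sites may recruit from their existing database (section 3.4).
- Sites should not register more Control than Test subjects (section 5.1).
- Once one lens group is full, enrolment continues only for the other (section 3.4).

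If the gap does differ and ratings change with wear, adaptation and early survivorship would be read as a lens effect. The 2-week odds ratio is formally tested, and the 2-week rating is one of three that feed the overall odds ratio of the primary test.

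**Working it through.** The plan gives no calculated figure to reproduce here; the windows are definitions.

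**Inputs**

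- D, questionnaire day counted from Visit 1: 10–30, 110–150 and 345–395 (section 4.1, Table 2).
- W, time from starting the lens to Visit 1: 0 to 2 months (section 3.2; section 3.4 for Test). Two months is taken as 61 days, with 59 to 62 as the calendar range.

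**Formula.** Elapsed time since starting the lens is T = W + D. Its minimum is 0 plus the window start, and its maximum is 61 plus the window end.

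| Rating | Minimum T | Maximum T | Maximum if W is at most 59 or 62 | Width of T | Width of stated window |
|---|---|---|---|---|---|
| 2-week | 0 + 10 = 10 | 61 + 30 = 91 | 89 or 92 | 91 − 10 = 81 | 30 − 10 = 20 |
| 4-month | 0 + 110 = 110 | 61 + 150 = 211 | 209 or 212 | 211 − 110 = 101 | 150 − 110 = 40 |
| 12-month | 0 + 345 = 345 | 61 + 395 = 456 | 454 or 457 | 456 − 345 = 111 | 395 − 345 = 50 |

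**Relative size.** Against the nominal time point, the largest prior wear is 61/14 = 4.4 times at two weeks, 2/4 = 50% at four months and 2/12 = 17% at twelve months. The issue is therefore mainly one for the 2-week rating.

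**From spread to bias.** To a first approximation, the confounding in the log odds ratio at a given period is

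b × (mean W in Test − mean W in Control),

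where b is the change in log odds of a positive rating per extra day on the lens at that period. If either factor is zero there is no bias from this source. The documents give neither b nor the distribution of W in either arm, so neither sign nor size can be computed.

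**Two limits on the range**

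- T is elapsed time. Part-time wear is allowed, and section 3.4 limits time since prescription and supply rather than wear, so days actually worn can be fewer.
- Criterion 1 can be read as applying the two-month limit only to subjects who are not neophytes. Section 3.4 applies it to all Test wearers but states no equivalent for Control, so on that reading W has no stated upper limit for Control neophytes.

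**The case against.** The strongest reply is that registration is a coherent time origin for a registry that does not fit lenses for study purposes (section 3.1), and that the plan uses it consistently. That stands: sections 2.2 and 4.1 and Table 2 all count from Visit 1, so there is no contradiction and the periods need no relabelling.

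A reader might also infer several stronger things that the documents do not support.

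- *That the start date is not recorded.* Section 7.2 summarises the fields, but the questionnaire forms are not visible in the public documents. Sites must also judge recency to answer criterion 1. All that can be said is that no such date is among the listed fields.
- *That the analysis is unadjusted for time on lens.* It is not a named term, but the propensity covariates are left open and section 14.1 defers detail to a stand-alone SAP that is not included. It may yet be used.
- *That the arms do differ, by up to two months.* The two-month rule in criterion 1, the windows and fitting before Visit 1 are written for both arms, and the database sentence in section 3.4 covers all subjects. A 61-day difference in means would need essentially all of one arm at day 0 and all of the other at the limit. An imbalance is possible but not shown.
- *That the sample size is undermined because Table 3 comes from about two weeks of wear.* Section 14.2 assumes constant response proportions over time, so on the plan's own assumption a later first rating leaves the calculation unchanged.

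The broad commitment in sections 4.2 and 14.5 to reduce baseline bias helps only if the variable exists. If the date is not captured, analysts cannot add it to the propensity score later from the listed fields.

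**Conclusion.** The point holds as a gap in design and analysis. The rules allow time since starting the lens to lie between about 10 and 91 days at the 2-week rating, 110 and 211 days at 4 months, and 345 and 456 days at 12 months. These limits assume two months is 61 days and that the two-month limit applies to every subject.

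Prior time on lens is a plausible confounder in this non-randomised comparison, mainly for the 2-week test and only diluted in the overall odds ratio. Whether it biases the result depends on a difference between arms and on a trend of ratings with wear, neither of which the documents quantify. It should be treated as an inexpensive safeguard, not as evidence that the comparison is biased.

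**What to change.** 1. In section 7.2, step 1.7, add the date of first wear (or of dispensing) of the new lens to the ECP Registration Questionnaire, if the form does not already hold it.
2. In section 14.1, add days on lens at Visit 1 to the baseline tables by arm, so that any imbalance is visible.
3. In section 14.5, name days on lens at Visit 1 as a covariate in the propensity score.
4. Optionally, repeat the 2-week comparison in subjects registered soon after starting the lens, with the cut-off stated and justified before database lock.

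The cost is one extra field at Visit 1 and one extra covariate. The sample size, visit windows and time origin stay as they are. If the form already collects the date, only steps 2 and 3 are needed.

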4.2. Study Design Rationale

The study is designed as an observational, prospective, non-interventional, multi-center, multi-national post-market study to evaluate the effectiveness of ACUVUE® OASYS with Transitions™ over a period of one year in the general population of spherical contact lens wearers and under general clinical practice. By allowing wide subject eligibility criteria, wide age range and different clinical practices from different countries, the study is ideal for obtaining real world data to assesses the effectiveness of this new technology.

This a non-randomized study and the sponsor has no control of the treatment assignment. The Test and Control groups may have large differences on their baseline characteristics, and these differences can lead to biased estimates of treatment effects. Appropriate statistical methods will be used to reduce the bias (see Section 14 for more details).

4.3. Subject Numbers

The study will enroll approximately 300 (maximum: 330) subjects in each arm with the intent of completing at least 240 in each arm. Thus, the study will enroll approximately 600 subjects with a maximum of 660 (Figure 1).

Multiple sites in the UK, Netherlands, Spain, and Germany will participate with other countries a possibility. Each site will enroll approximately similar numbers of test and control subjects.

4.4. Study Duration

Study enrollment occurs with execution of the study-related forms and informed consent. Study completion occurs with completion of the 12-month survey.

Once the Test lens is launched in the study-participating country, the first subject registration will occur within six (6) months.

The enrolment period should not exceed twelve (12) months in any country without prior authorization from the Sponsor.

Subjects will present to the investigational site for Visit 1. Follow-up assessments are performed online at approximately 2-weeks, 4-months, and 12-months following Visit 1. Therefore, each subject is enrolled in the study for approximately 12 months. With the 12-month enrollment period, the study will last approximately two (2) years per country.

5. TEST ARTICLE ALLOCATION AND MASKING

5.1. Test Article Allocation

This is a non-randomized observational study. Subjects receiving a new lens brand as part of the routine practice at the investigational site will be asked to participate:

- Subjects receiving an ACUVUE® OASYS with Transitions™ contact lens on both eyes will comprise the Test group.
- Subjects receiving any other spherical silicone hydrogel lens to be worn as daily wear and frequent replacement (2-weekly or monthly) will comprise the Control group.
- The Test/Control allocation per site is approximately 1:1. Sites should not recruit a larger number of control subjects than test subjects.

5.2. Masking

This is an open label registry study. The identity of the lenses is known to all. Given this, there are no procedures for maintaining and breaking the masking.

6. STUDY INTERVENTION

6.1. Identity of Test Articles

The following contact lenses will be used in this study:

Table 1: Study Lenses

	Test	Control
Name	ACUVUE® OASYS with Transitions™	
Manufacturer	Johnson & Johnson	
	Commercial	Any reusable spherical silicone hydrogel brand that is approved and marketed in the country conducting the study.
Lens Material	senofilcon A	
Nominal Base Curve @ 22°C (mm)	8.4, 8.8	
Nominal Diameter @ 22°C (mm)	14.0	
Nominal Distance Powers (D)	+8.00 through -12.00	
Water Content (%)	38	
Center Thickness (mm)	0.085	
Oxygen Permeability (Dk)	103	
Packaging Form (vial, blister, etc.)	Sterile blister pack	
Wear Schedule in Current Study	DW	DW
Replacement Frequency	2 weeks or as recommended by ECP	2 weeks/monthly
Photochromic Additive	Yes	No

6.2. Ancillary Supplies/Products

[figure not shown]
None specified. Subjects may use any approved and marketed contact lens care products or wetting drops that would normally be prescribed by the investigator in their country of practice. Care products initially recommended by the ECP will be tracked.

